### **Histopathology**

This part is to determine changes of eccrine gland lobules as a reduction in size, destruction or marked atrophy with molecular and immunofluorescence methods. In addition we will investigate the skin inflammation (type of immune cells, fibrosis).

The participants of this substudy have to sign a separate informed consent document for taking the skin biopsies.

### **8.2.2 Assessment of Secondary Outcomes**

For all persistent isolated microorganisms after PTD and antisepsis preparation of the skin will be subjected to whole genome sequencing for phylogenetic analysis based on core genome single nucleotide polymorphisms. To do so, chromosomal DNA of isolated bacteria will be extracted using the DNeasy UltraClean Microbial Kit (QIAGEN, Hilden, Germany) according to the manufacturer's instructions. DNA library preparation is performed using the QIASeq FX Kit (QIAGEN). Pooled libraries will be sequenced on an Illumina MiSeq (paired-end sequencing, 2 x 150 bp reads, 50-fold coverage). Raw sequencing data (FASTQ) will be processed using trimmomatic (41). Trimmed sequencing reads are assembled to CONTIGS using SPAdes (42). Core genome single nucleotide polymorphisms (SNPs) are determined by analyzing CONTIGS with parSNP (43). Concatenated SNPs are transformed into a multi-alignment file which eventually serves for the calculation of a phylogenetic tree by maximum likelihood (44). Whole genome sequencing, assembly and phylogenetic comparisons will be done at the Institute of Medical Microbiology (IMM) at the University of Zurich.

What	When	How
Whole Genome Sequencing/Phylogeny	After termination of all study participants	In collaboration with the Institute for Clinical Microbiology with a lot of experience in this field

### **8.2.3 Assessment of Safety Outcomes**

#### **8.2.3.1 Serious Adverse Events**

Recording of serious adverse event (SAE) information time of onset, duration, resolution, action to be taken, assessment of intensity, and relationship with study intervention.

#### **8.2.4 Assessments in Participants who prematurely Stop the Study**

Participants who are withdrawn from the study prematurely due to adverse event, will be followed-up until adverse-effects disappeared. Follow up may include but is not limited to physical examination, laboratory tests, vital signs, telephone calls. Outcomes and resolution of events will be recorded in the Case Report Forms. In case of lost to follow up, efforts will be made to contact the patient or to ascertain the vital status of the participant.

### **8.3 Procedures at Each Visit**

#### **8.3.1 Screening Visit = Visit 1**

*Screening visit, Day – at least -7 days before the study start*

- Information of the study and all necessary study visits
- Check for In- and Exclusion criteria

- Enrollment if agree to participate in study
- Enter basic demographic parameters in electronic CRF (age, sex, current medications, and underlying diseases)
- Scheduling of all study visits

Duration: ca. 30 minutes

Location: Division of Infectious Diseases, University Hospital Zurich

**Study schedule:**

Substudy in 5 volunteers:

In the course of the study a total of three small skin biopsies are taken (3mm diameter each) from 5 volunteers. The time and locations of the performed biopsies will be

1. from the right groin immediately after the MAL-PDT or at day 7
2. from untreated control area in the left groin after the MAL-PDT(day 0 or 7)
3. from the MAL-PDT area on day 21 as the control after treatment.

**8.3.2 Visit 2 = Day 1 of the study**

On day 1 with [name] and [name], a skin scraping of the groin will be performed and sent for microbiological culture. Then, 5% topical methyl aminolevulinate (MAL) as the photosensitizer will be applied for 3 hours under occlusion in the right groin of the patient. After the incubation, the photodynamic process will be started by irradiation of the area with 40J/cm^2 red light from a 633nm emitting LED during 13 minutes.

Immediately after the MAL-PDT, skin antisepsis will be performed. Antisepsis of the skin is performed with a povidone-iodine/alcohol solution (Betaseptic®, Mundipharma, Limburg, Germany) and repeated three times for a total duration of 3 minutes to imitate standard surgical antisepsis before a hip arthroplasty surgery.

For all inguinal swabs, we will use the scratching method using a scalpel as already applied in a previous study (ethical approval BASEC-Nr 2016-01017). The swabs will be sent to the microbiology laboratory of the University of Zurich for bacterial analysis (analysis under supervision of Prof. [name]).

Skin biopsies will be done as a routine procedure at the Department of dermatology.

In short:

- Inguinal skin scraping before PDT
- Natural bacterial porphyrin fluorescence photography
- Study intervention: Photosensitizer application for 3 hours
- PDT for 15 minutes
- Inguinal skin scraping
- Skin antisepsis with povidone/iodine (3x times for 1 minute)
- Inguinal skin scraping
- Punch biopsies in 5 participants
- Documentation of adverse effects

Duration: 4 hours

Location: Department of dermatology, University Hospital Zurich

**8.3.3 Visit 3 (day 7±3)**

Skin scraping after skin antisepsis will be repeated 7 days later and analyzed for bacterial cultures.

In short:

- Inguinal skin scraping

- Skin antisepsis
- Inguinal skin scraping
- Punch biopsies in 5 participants
- Documentation of adverse effects

**Duration:** 30 - 60 minutes

**Location:** Department of dermatology or Infectious Diseases, University Hospital Zurich

#### **8.3.4 Visit 4 (day 21±7)**

Skin scraping after skin antisepsis will be repeated 21 days later (study visit day 21) and analyzed for bacterial cultures.

In short:

- Inguinal skin scraping
- Skin antisepsis
- Inguinal skin scraping
- Punch biopsies in 5 participants
- Documentation of adverse effects

**Duration:** 30 -60 minutes

**Location:** Department of dermatology or Infectious Diseases, University Hospital Zurich

#### **8.3.5 Visit 5 = End of Study Visit (day 35±7)**

On day 35 ( $\pm 7$  days) of the study, volunteers will be seen for the last study visit to ask for side effects and to inform about the individual study result.

In short:

- End of study
- Documentation of adverse effects
- Information of the individual study results

**Duration:** 30 minutes

**Location:** Division of Infectious Diseases, University Hospital Zurich

## **9 SAFETY**

During the entire duration of the study, all serious adverse events (SAEs) that may be causally related to the study intervention are collected and documented in source documents. Reportable events are recorded in the case report form (CRF). Study duration encompassed the time from when the participant signs the informed consent until the last protocol-specific procedure has been completed, including a safety follow-up period.

In order to guarantee participants' safety and health, further adverse events which must be documented or reported are to be designated in the protocol or at the request of the responsible CEC.

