## **9.2 Recording and Assessment of Serious Adverse Events**

The investigator has the responsibility for SAE identification, documentation, and assessing the causal relationship study intervention.

All SAEs will be fully documented in the appropriate eCRF. For each SAE, the investigator will provide the onset, duration, treatment required, outcome and action taken with regard to the study intervention.

The assessment by the investigator with regard to the study intervention relation is done according to the following definitions:

Unrelated	

• The event started in no temporal relationship to the medical intervention applied and

• The event can be definitely explained by underlying diseases or other situations.

Related	

• The event started in a plausible temporal relationship to the medical intervention applied and

• The event cannot be definitely explained by underlying diseases or other situations.

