### **10.3.5 Safety Analysis**

Analysis of SAE as standard (number of adverse and serious adverse events)

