### 12.1.2 Specification of Source Documents

The following documents are considered source data, including but not limited to:

- SAE worksheets
- Nurse records, records of clinical coordinators, and

Source data must be available at the site to document the existence of the study participants and substantiate the integrity of study data collected. Source data must include the original documents relating to the study, as well as the medical treatment and medical history of the participant.

The following information (at least but not limited to) should be included in the source documents:

- Demographic data (age, sex)
- Inclusion and Exclusion Criteria details
- Participation in study and signed and dated Informed Consent Forms
- Visit dates
- Microbiological data (identification of bacteria)
- SAEs (related) and concomitant medication
- Reason for premature discontinuation

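### Section 9 limits SAE collection to possibly related events, contradicting Section 9.2, the annual safety report and the safety analysis; separately, the Section 9.2 causality classes are not exhaustive

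*Combined protocol and SAP*

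**What the plan says.** **Collection.** The opening of Section 9 states that "all serious adverse events (SAEs) that may be causally related to the study intervention are collected and documented in source documents". The next sentence reads "Reportable events are recorded in the case report form (CRF"). The same paragraph defines the study duration as running from consent through a safety follow-up period.

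**Documentation and use.** Section 9.2 says "All SAEs will be fully documented in the appropriate eCRF" and then asks the investigator to assess the relation to the intervention. Section 8.2.3.1 lists that relation among the items recorded for an SAE. The Annual Safety Report paragraph in Section 9.3 covers all SAEs. Section 10.3.5 describes the safety analysis as the "number of adverse and serious adverse events". Section 9.1 defines adverse events without regard to cause. Section 12.1.2 names "SAEs (related) and concomitant medication" among the items to be held in source documents.

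**Causality classes.** Section 9.2 has two, each formed by two conditions joined by *and*. *Unrelated* needs no link in time with the intervention together with "The event can be definitely explained by underlying diseases or other situations". For the class *Related*, the requirement is plausible timing together with "The event cannot be definitely explained by underlying diseases or other situations". There is no third class and no default.

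**The concern.** Sections 9 and 9.2 give different rules for the same events. Under Section 9, relatedness decides whether an SAE is collected at all. Under Section 9.2, relatedness is a judgement made on an SAE already in the database. A site that follows Section 9 to the letter cannot supply what Section 9.2, the annual report and Section 10.3.5 ask for.

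The order matters because the study is open label (Section 5.1). An SAE set aside at the collection step would have been judged by someone who knows what the participant received, and it need leave no entry for anyone else to review. The internal monitoring in Section 12.3 includes a check of SAEs, but it cannot check one that was never written down. At stake is the SAE count in a study of healthy volunteers that has safety evaluation as a stated objective (Section 3.4) and may lead to a trial in patients having hip arthroplasty (Section 5.1).

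The gap in the causality classes is a separate matter. It acts when a recorded SAE is classified, not when it is collected.

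**Working it through.** No figure in the plan can be reproduced here, since no expected number of SAEs is given. The check is a comparison of the rules and an enumeration of the Section 9.2 definitions.

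**Step 1. The rules side by side.**

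| Place | SAEs covered | Causality limit |
|---|---|---|
| Section 9, collection | Those possibly caused by the intervention | Yes |
| Section 9, CRF entry | Reportable events | Yes, if read with the Section 9.3 reporting test |
| Section 9.2, eCRF | All | No |
| Section 9.3, report to the ethics committee | Those for which attribution cannot be ruled out | Yes, for reporting |
| Annual Safety Report | All | No |
| Section 10.3.5, safety analysis | AEs and SAEs, counted | No |
| Section 12.1.2, source documents | Related SAEs named, in a minimum list | Not a restriction |

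The restrictive side rests on the two Section 9 sentences. A filter on reporting (Section 9.3) is compatible with recording everything; a filter on collection is not. The *Unrelated* class in Section 9.2 also has little purpose unless SAEs judged unrelated reach the eCRF.

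**Step 2. Are the Section 9.2 classes exhaustive?** Take timing as plausible or absent, and another definite explanation as present or absent: 2 × 2 = 4 combinations.

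| Timing | Definite other explanation | Class |
|---|---|---|
| Absent | Present | Unrelated |
| Plausible | Absent | Related |
| Plausible | Present | None |
| Absent | Absent | None |

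Two of the four combinations have no class. The third row is a realistic case: an intercurrent illness with its own clear cause that begins during the weeks of follow-up.

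**Step 3. Does this say how many events are affected?** No. Let *t* be the probability that timing is plausible and *e* the probability of a definite other explanation. If the two are independent (an assumption), the unclassified share is *t·e* + (1 − *t*)(1 − *e*).

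- *t* = 0.1, *e* = 0.1: 0.01 + 0.81 = 0.82
- *t* = 0.5, any *e*: 0.5*e* + 0.5(1 − *e*) = 0.50
- *t* = 0.9, *e* = 0.1: 0.09 + 0.09 = 0.18

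With both probabilities anywhere from 0.1 to 0.9 the share runs from 18% to 82%. The documents contain nothing to narrow that range.

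**The case against.** The best defence is that little would be lost in practice.

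- **Parallel collection.** Adverse effects are documented at visits 2 to 5 (Sections 8.3.2 to 8.3.5). The Section 8.1 study plan lists serious and other adverse events at days 7, 21 and 35. Section 4.3 records unexpected signs and symptoms as yes or no. Section 8.2.4 follows participants withdrawn for an adverse event and puts the outcome in the CRF. None of these states a causality filter. This stands, and it makes loss a possibility rather than a consequence. It does not settle which SAEs enter the CRF and the Section 10.3.5 count.
- **A low threshold.** Section 9 asks whether an SAE may be related, not whether it is. This stands: only SAEs thought incapable of being related would drop out. The judgement still precedes the record.
- **Section 12.1.2.** A reader might infer that it bars unrelated SAEs from source documents. It does not: the list is introduced as a minimum. It is an inconsistency in wording, not evidence of a filter.
- **Reporting is covered.** Section 9.3 has its own test, so an SAE that fits neither Section 9.2 class still has a reporting rule. This stands.
- **Category A.** Minimal risk (Section 1.8) might justify limited collection. Even so, the protocol should state one rule, and at present it states two.

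**Conclusion.** The contradiction is in the current text, and so is the gap in the Section 9.2 classes. Both should be repaired, and the point is minor. It does not touch the microbiological primary outcome, and the safety outcomes in Section 4.3 do not depend on the Section 9 sentences.

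The effect on the SAE count cannot be quantified. The documents give no expected number. I assume few or none, from the minimal-risk classification and the healthy population, so any change in the count would be correspondingly small.

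Two stronger readings are tempting. A reader might infer that half of all SAEs would go unclassified; the result is two of four logical combinations, and the share of events is unknown. A reader might also infer that the Section 9.2 gap lets harms be screened out before recording; only Section 9 could do that, because the Section 9.2 definitions apply to SAEs which that section says are already documented.

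The four-way count assumes that absent and plausible timing are the only two options, as the definitions suggest.

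**What to change.** **Section 9.** Replace the restriction to possibly related SAEs, and the sentence limiting CRF entry to reportable events, with one rule: every SAE during the study duration already defined there (consent to the end of safety follow-up) is recorded in source documents and the eCRF whatever its suspected cause, in PDT participants and in the control participants described in Section 5.2, and causality is assessed afterwards.

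**Section 9.2.** Make the classes exhaustive. One way is to class an SAE as unrelated only if it meets both existing conditions for that class, and every other SAE as at least possibly related. An added intermediate class would also close the gap.

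**Section 12.1.2.** Delete the bracketed word limiting SAEs to related ones, for consistency.

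**Leave unchanged.** The AE definition in Section 9.1, which starts at the intervention, and the Section 9.3 reporting filter. Neither conflicts with the new rule, since the SAE definition in Section 9.1 is not tied to the intervention and reporting is a later step than recording.

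**Cost.** A protocol wording change and a few more eCRF entries.

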### **Serious Adverse Event**

A serious adverse event is defined as any event which:

- requires inpatient treatment not envisaged in the protocol or extends a current hospital stay;
- results in permanent or significant incapacity or disability;
- is life-threatening or results in death; or
- causes a congenital anomaly or birth defect.

## **9.2 Recording and Assessment of Serious Adverse Events**

The investigator has the responsibility for SAE identification, documentation, and assessing the causal relationship study intervention.

All SAEs will be fully documented in the appropriate eCRF. For each SAE, the investigator will provide the onset, duration, treatment required, outcome and action taken with regard to the study intervention.

The assessment by the investigator with regard to the study intervention relation is done according to the following definitions:

Unrelated	

• The event started in no temporal relationship to the medical intervention applied and

• The event can be definitely explained by underlying diseases or other situations.

Related	

• The event started in a plausible temporal relationship to the medical intervention applied and

• The event cannot be definitely explained by underlying diseases or other situations.

## **9.3 Reporting of Serious Adverse Events**

If, in the course of a clinical trial, serious adverse events occur in participants in Switzerland, and it cannot be excluded that the events are attributable to the intervention under investigation, the investigator must report these events:

- to the CEC **within 15 days**.

### **Safety and protective measures**

If immediate safety and protective measures have to be taken during the conduct of this clinical trial, the investigator must notify the CEC of these measures, and of the circumstances necessitating them, **within 7 days**.

### **Annual Safety Report**

All SAEs will be summed up in the **annual safety report (ASR)** and submitted to the CEC. ASR shall contain:

- A summary of events including severity and causal relationship to the intervention and on the safety of participants.

- The accompanying letter provided with the Annual Safety Report should contain a short summary of the status of the clinical trial in Switzerland (number of centers open/closed, number of patients recruited/recruitment closed, and number of SAEs).

## 9.4 Follow up of (Serious) Adverse Events

Participants terminating the study (either regularly or prematurely) with

- reported ongoing SAE, or
- any ongoing AEs of laboratory values or of vital signs being beyond the alert limit

will return for a follow-up investigation. This visit will take place up to 30 days after terminating the treatment period. Follow-up information on the outcome will be recorded on the respective SAE page in the eCRF.

# 10 STATISTICAL METHODS

Categorical data will be tested for differences using Fisher's exact or chi-squared tests, as appropriate, whereas continuous variables will be tested using Wilcoxon rank sum tests.

## 10.1 Hypothesis

We hypothesize that photodynamic treatment improves skin antisepsis by reduction of persistent skin colonizing bacteria through the destruction of the sebaceous and sweat glands and by its bactericidal effects.

## 10.2 Determination of Sample Size

Aim: 20 volunteers to show the effect of PDT in healthy volunteers.

## 10.3 Planned Analyses

- As a pilot study, we plan to do descriptive statistics only.
- Categorical date will be tested for differences using Fisher's exact or chi-squared tests.
- Continuous variables will be tested using Wilcoxon rank sum tests.
- Data will be analyzed using Stata® version 14.2 (Stata Corporation, College Station, TX). Two-tailed P-values <0.05 are considered statistically significant.

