#### 3.2 Primary Objective

Here we use skin swabs from the groin before and after Photodynamic treatment. For all these swabs, we will use the scratching method using a scalpel as already applied in a previous study (ethical approval BASEC-Nr 2016-01017). The skin swabs will be sent to the microbiology laboratory of the University of Zurich for bacterial analysis.

We distinguish between an immediate (day 0) and long-term effect (3 weeks) investigating the skin microbiome after PDT.

In Detail:

1. Immediate effect of photodynamic treatment in combination with surgical antisepsis on bacterial skin colonization
  - 1.1. To quantitatively evaluate bacterial density and species before photodynamic treatment and after photodynamic treatment and antisepsis skin preparation
    - 1.1.1. **Parameter:** growth of bacteria (yes/no), number and identification of bacteria (species name), semiquantitative amount of bacteria
2. Long-term effect on bacterial skin colonization in the groin after photodynamic treatment
  - 2.1. To quantitatively evaluate bacterial density and species before and after 7 and 21 days of photodynamic treatment
    - 2.1.1. **Parameter:** growth of bacteria (yes/no), number and identification of bacteria (species name), semiquantitative amount of bacteria
  - 2.2. To evaluate changes of sebaceous and sweat glands after photodynamic treatment on skin biopsies
  - 2.3. **Parameters:** Number and size of glands

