#### **Study schedule:**

On day 0 with [name] and [name], a skin scraping of the groin will be performed and sent for microbiological culture. Then, 5% topical methyl aminolevulinate (MAL) as the photosensitizer will be applied for 3 hours under occlusion in the right groin of the patient. After the incubation, the photodynamic process will be started by irradiation of the area with 40J/cm^2 red light from a 633nm emitting LED during 13 minutes.

Immediately after the MAL-PDT, skin antisepsis will be performed. Antisepsis of the skin is performed with a povidone-iodine/alcohol solution (Betaseptic®, Mundipharma, Limburg, Germany) and repeated three times for a total duration of 3 minutes to imitate standard surgical antisepsis before a hip arthroplasty surgery. Skin scraping will be repeated after the 3rd antisepsis and 7 and 21 days later (study visit day 7 and 21) for bacterial cultures.

As a control group, we will take skin swabs before and after skin antisepsis without PDT in 10 participants.

On day 35 ( $\pm 7$  days) of the study, volunteers will be seen for the last study visit to document any adverse effects and to inform about the individual study result.

Substudy in 5 volunteers:

In the course of the study a total of three small skin biopsies are taken (3mm diameter each) from 5 volunteers. The time and locations of the performed biopsies will be

1. from the right groin immediately after the MAL-PDT or at day 7
2. from untreated control area in the left groin after the MAL-PDT (day 0 or 7)
3. from the MAL-PDT area on day 21 as the control after treatment.

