#### 7.1.2 Control Intervention

No control intervention in this study

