## 7.2 Administration of Study Intervention

### 7.2.1 Study Intervention

Details of study Intervention	Justification
1. Inguinal skin scraping before photodynamic treatment	Baseline microbiome data
2. Natural bacterial porphyrin fluorescence photography	Baseline fluorescence photography
3. Photosensitizer application, followed by fluorescence photography Photodynamic therapy (PHT) (1x) over 15 minutes at the dermatology ward	Treatment to kill bacteria and to reduce glands in order to reduce colonization bacteria
4. Skin antisepsis in the groin, skin scraping after antisepsis	To measure bacterial colonization to know the immediate effect of PDT
5. Punch biopsy  specimen of the MAL-PDT area (immediately after PDT) and of an untreated area as a control	To analyze size and structure of glands in the skin
6. Inguinal skin scraping and punch biopsy of the MAL-PDT area after 7 and 21 days	To measure bacterial colonization to know the long-term effect of PDT

 only in 5 participants

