## Microbiology

In short, the patient's sample swabs will be streaked out onto Columbia sheep blood agar plate without antibiotics (bioMérieux, Marly-l'Etoile, France), colistin-nalidixic acid (CNA) blood agar (bioMérieux) plate for aerobic cultivation and a Brucella plate (in-house sheep blood agar plates with hemin and vitamin K1) for anaerobic cultivation using GENbag (bioMérieux). Final identification will be done by matrix-assisted laser desorption ionization-time of flight mass spectrometry spectrometry (MALDI-TOF MS) using a Bruker MALDI Biotyper. The amount of bacteria will be semiquantitative described as +, ++, +++ based on growth on agar plates. All cultured microorganisms will be stored in skim milk at -80C° for potential subsequent analysis by whole genome sequencing for analyzing the secondary outcome.

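### On a plain reading the plan tests the ordered density grade as unordered categories, and no named test uses the before/after pairing

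*Combined protocol and SAP*

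**What the plan says.** Section 3.2 lists the parameters of the primary objective as "growth of bacteria (yes/no), number and identification of bacteria (species name), semiquantitative amount of bacteria". The Microbiology text in 8.2.1 fixes the scale of the last one: "The amount of bacteria will be semiquantitative described as +, ++, +++ based on growth on agar plates". With no growth, that makes four ordered levels.

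Section 10.3 offers two test rules. One is "Categorical date will be tested for differences using Fisher's exact or chi-squared tests"; the other is "Continuous variables will be tested using Wilcoxon rank sum tests". Section 10 and the synopsis repeat both. The grade is not assigned to either rule by name, and no paired, trend or baseline-adjusted method appears.

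A pre-treatment sample exists for everyone. Section 8.3.2 schedules "Inguinal skin scraping before PDT", which the table in 7.2.1 labels "Baseline microbiome data". For controls, 5.2 says: "As a control group, we will take skin swabs before and after skin antisepsis without PDT in 10 participants".

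Section 10.3.2 makes the primary analysis a descriptive before/after comparison. Section 10.3 says the statistics will be descriptive only, then sets a two-tailed 0.05 significance threshold.

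**The concern.** A Fisher or chi-squared test on a 2 x 4 table gives the same answer however the columns are arranged. A shift from +++ to + counts no more than any other rearrangement. With 10 to 20 people per group, that can hide a fall in density which a rank-based test would detect in the same data.

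The before/after comparison has a second problem. Fisher, chi-squared and rank-sum tests all treat the before and after grades as coming from different people. If a person's grades are correlated, information already collected is discarded, and it is discarded in the comparison that the plan calls primary.

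The results are meant to decide whether a hip-arthroplasty trial follows (2.1, 5.1), so a missed or poorly described shift in density has consequences.

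**Working it through.** **What the plan gives.** Two-sided alpha 0.05 (10.3); 20 volunteers (10.2); 10 controls (5.2). Section 7.1.1 gives PDT to 20, which implies 20 v 10. If the 20 volunteers include the controls, the split is 10 v 10. Both are shown. No effect size, grade distribution, within-person correlation or power is stated, so there is no figure of the plan's to reproduce. All distributions below are assumptions.

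**1. Order, PDT v control.** For 10 people on four grades there are C(13,3) = 286 possible tables; for 20 there are C(23,3) = 1,771. That gives 286 x 286 = 81,796 pairs of tables (10 v 10) or 1,771 x 286 = 506,506 (20 v 10). For each pair, compute the exact 2 x 4 Fisher (Freeman-Halton) p-value and the exact conditional Wilcoxon rank-sum p-value with midranks. Power is the summed multinomial probability of the pairs with p < 0.05.

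| PDT v control, % none/+/++/+++ | 10 v 10: Fisher, Wilcoxon, gap | 20 v 10: Fisher, Wilcoxon, gap |
|---|---|---|
| 70/20/8/2 v 30/40/20/10 | 29.8, 37.4, 7.6 | 51.3, 56.3, 5.0 |
| 50/30/15/5 v 20/30/30/20 | 21.6, 33.3, 11.7 | 38.0, 47.9, 9.9 |
| 50/30/15/5 v 10/30/30/30 | 42.5, 59.8, 17.3 | 65.2, 76.9, 11.7 |
| 40/35/15/10 v 10/20/30/40 | 37.9, 54.3, 16.4 | 56.5, 71.0, 14.5 |

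The gap is 5 to 17 points. Simulations of the same cells scatter around these values, with gaps of 4 to 19. With both groups at the control distribution, both tests reject in under 5%.

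**2. The same check near the floor.** Let controls be 70/20/8/2 and the common odds ratio 8. The PDT sterile share is then found from odds 0.70/0.30 x 8 = 18.67, so 18.67/19.67 = 95%. Power is 9.8 v 10.2% (10 v 10) and 40.1 v 39.7% (20 v 10), Fisher v Wilcoxon. Order gains nothing here.

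**3. Pairing, before v after PDT (simulation).** Assumed baseline grades are 5/20/35/40. At odds ratio 4 the cumulative shares 5, 25 and 60% become:
- 0.0526 x 4 = 0.2105, so 17%
- 0.3333 x 4 = 1.333, so 57%
- 1.5 x 4 = 6, so 86%

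Follow-up grades are therefore about 17/40/29/14. The before/after correlation is set on a latent normal scale. There were 1,000 runs at n = 20 and 2,000 at n = 10. The Monte Carlo SE at 46% and 1,000 runs is sqrt(0.46 x 0.54/1000) = 1.6 points.

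| Correlation | n = 20: Fisher, rank-sum, signed-rank (%) | Fisher to signed-rank | n = 10: Fisher, rank-sum, signed-rank (%) | Fisher to signed-rank |
|---|---|---|---|---|
| 0 | 44.5, 61.1, 56.4 | +12 | 20.5, 33.9, 24.8 | +4 |
| 0.3 | 46.5, 66.1, 72.1 | +26 | 17.4, 29.5, 28.7 | +11 |
| 0.6 | 46.1, 69.6, 87.5 | +41 | 16.2, 27.7, 39.6 | +23 |

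The n = 20 gain has two parts. Order (Fisher to rank-sum) gives 17, 20 and 24 points. Pairing (rank-sum to signed-rank) gives -5, +6 and +18.

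The gain depends on the effect. At odds ratio 8 and n = 20, Fisher to signed-rank is 83.8 to 91.9, 83.1 to 95.8 and 89.2 to 99.3%, or 8 to 13 points. At odds ratio 2, n = 10 and correlation 0 or 0.3, the two are level (7.8 v 6.8%; 6.2 v 5.8%).

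**4. Baseline adjustment, PDT v control (simulation).** With 10 v 10, controls 25/25/25/25 and odds ratio 8, moving from the asymptotic rank-sum test to rank ANCOVA on baseline grade changes power from 65 to 62% at correlation 0. It stays at 65% at 0.3 and rises from 64 to 73% at 0.6.

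**The case against.** **The grade is never assigned to Fisher.** This is correct. Growth yes/no and species presence are the obvious targets of that rule. The mention of dilution plates in 4.1 could be read as yielding counts, and an analyst could apply the rank-sum test to the grade. So the assignment is the plain reading of a three-symbol grade, not a stated rule. This does not supply the missing pairing, and the text still needs a sentence saying which test applies.

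**The plan is descriptive and claims no power.** This is also correct. A reader might infer that the study loses power it had promised; it promised none. But the same list names tests and a significance threshold, so p-values are planned.

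**The loss may be small.** Section 2.4 makes sterile cultures the trigger for a larger study. If most post-antisepsis cultures are sterile, step 2 shows that order adds nothing between groups. A general claim that the density comparison loses power is therefore unsupported; the loss is conditional.

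**Baseline imbalance.** A reader might infer that adjusting for baseline must help PDT v control. Step 4 shows a gain only at a correlation clearly above 0.3, and a small cost at zero. Stratifying on four baseline grades is impractical with 10 to 20 per group.

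**PDT v control may not be intended.** Section 10 does not name it, and 7.1.2 says "No control intervention in this study". The remedy must therefore start with before/after.

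**Conclusion.** The point holds as a gap in the analysis specification that costs nothing to close. The density grade is ordinal, the plain reading sends it to tests that ignore order, and no named test uses the pairing in the primary comparison.

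Between groups, ignoring order costs about 5 to 17 points if 10 to 30% of controls are sterile, and about nothing if 70% are. For before v after at n = 20 and odds ratio 4, unpaired Fisher gives up 12 to 41 points against the signed-rank test. The upper end needs a correlation of 0.6. If the rank-sum test were used instead, the shortfall would be 6 to 18 points at correlations 0.3 to 0.6, with none at zero.

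These sizes rest on assumed grades, odds ratios and correlations. The direction does not depend on the plan having set a power target, and none of its figures is contradicted.

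**What to change.** In sections 10 and 10.3:

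- State that density is an ordinal outcome with four levels (none, +, ++, +++).
- For before v after PDT, use an exact Wilcoxon signed-rank test on the grade, stating how zero changes are handled, and McNemar's exact test for growth yes/no. Say which follow-up scraping is compared with the pre-PDT one, since 8.3.3 and 8.3.4 list scrapings both before and after antisepsis.
- For PDT v control, if intended, use an exact Wilcoxon rank-sum test on the grade, with a proportional-odds or rank-ANCOVA analysis adjusted for baseline grade as support. Use Fisher's exact test for unpaired yes/no data.
- Make estimates with 95% CIs the main pilot output: the shares of participants whose grade falls or rises and, between groups, the probability that a PDT participant has a lower grade than a control.
- Reconcile the descriptive-only statement with the 0.05 threshold, and the control-group and group-size statements in 5.2, 7.1.1 and 7.1.2.

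The cost is a few sentences and no new data. One small downside is that the pairing and the baseline adjustment can each lose a few points of power if before and after grades are uncorrelated (about 5 and 3 points in the cases above).
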